The CV toolkit is an innovative care model that is proactive, patient-centered and personalized to each woman that comes to an appointment. A patient begins using the CV toolkit at check-in for her appointment when she is given the CV worksheet to fill out while waiting to see her provider. Patient education materials specifically on women and CV risk will be in the waiting room and exam rooms. The CV worksheet will be used to initiate the provider-patient discussion of CV risk, and her provider or another staff member will use the information to fill out the CV template in CPRS during or after the appointment. Depending on the site needs and preferences, a research assistant and/or the *Gateway* facilitator may help populate the CV template with the screener information. The patient and provider will collaboratively determine the next steps (i.e. *Gateway to Healthy Living*, other referral, or waiting) and the provider will document the action plan in the template. All participants will be offered the *Gateway to Healthy Living* program by providers or other staff member as engagement and support for the patient action plan.

After the appointment, each woman will be asked if she is willing to participate in the project for monitoring CV risks and choices and if she consents, she will complete a patient survey and a possible interview with the RA (every 3rd consented patient will be asked to participate in both a survey and interview). At the sites where it is not feasible to consent a woman immediately after her appointment, the research staff will generate a patient list of all women seen in the clinic who had a CPRS template activated during her visit. Based on that list, a sample of the women will be mailed a consent and survey (and every 3rd consented patient will be asked to participate in the interview). Follow-up surveys and interviews will be administered to all women who completed the baseline survey six months after the baseline survey.

Those women who are referred to the *Gateway to Healthy Living* program will be contacted by the program facilitator immediately to arrange the group meeting. The women will be considered engaged in the *Gateway to Healthy Living* program when she attends the first group meeting. Information on goal setting, behavior change intentions and participation in other services will be collected by the facilitator at the group meeting and at the follow-up phone calls.

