Research staff will meet with their local study supervisor (the Site Lead or the Project Director) on a weekly basis for supervision, ongoing monitoring of interactions with subjects, and problem solving. Research and clinical staff are trained to identify events that would fall under mandatory reporting guidelines, such as harm to self or others. The PI will be available at all times by cell phone. When the PI is not available, the PI will delegate this responsibility to another qualified, credentialed staff member.

*Data safeguards.* Before analysis of the data, all identifying information will be removed from the data. No information that could identify study subjects will be published or presented. Data will be reported only in the aggregate. Identifiable data will be stored separately from coded data sets. Access to identifiable study data will be restricted to research team on a need-to-know basis.

*Discomfort with assessment, intervention procedures or disclosure safeguards.* During the course of participation in the study, a subject could feel uncomfortable answering the survey or interview questions. All interviewers will be trained in the assessments and with sensitivity to the issues to be discussed. All subjects are informed that they may choose to skip any questions that they find uncomfortable or withdraw from the study at any time.

For patients who consent to be surveyed, the 30-minute surveys delivered in person by the RA will occur in a private room in the VA clinic setting at each site. Since some patients may not attend the group immediately or at all, patient baseline survey packets with an information sheet will be sent to the patient's mailing address in CPRS/VISTA. Patients who agree to the survey, by completing the survey, will have a VA addressed stamped envelope to return the survey document. For the subset of women selected for the patient interviews, the interviews will be conducted by telephone, but could be done in person (at the medical center) if the patient prefers in-person. Staff interviews will be conducted in person in a private room in the VA clinic setting or by telephone at each site.

Response procedures for adverse events are described in Section 6 Reporting (below).

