**Quantitative Analysis:** We will use descriptive and inferential statistics to understand variations in the measures described above. For patients, we will conduct bivariate analysis to examine variations in outcomes (CV risk factor control, cardiac event or procedure, etc.) by those who participated in the *Gateway to Healthy Living* program, versus those who received a referral to a different program/service, and those who received no referral. For providers, we will examine differences in their patient panel (e.g. those with CV risk factors under control at follow-up) by their engagement in the CV toolkit program. To evaluate the CV toolkit, we will use the nonrandomized stepped wedge design, a generalized mixed model coupled with an allowance for nonrandom effects, to evaluate the implementation across the providers at four sites. The intervention will be defined as “turning on” when a provider first engages in the CV toolkit (first

uses the CV template). We will model the effect of the implementation of the CV toolkit intervention on referral rates, while controlling for organizational level, provider level and patient level covariates.

**Impact-focused evaluation:** Secondary aims focus on factors that empower Women Veterans to engage in and benefit from care. We will use generalized linear mixed models (GLM) to evaluate a) cross-sectional relationships of patient activation, health-related quality of life, and care experiences at enrollment, with provider and site characteristics, adjusting for patient social and demographic characteristics; and b) prospective changes in patient activation, health-related quality of life, and care experiences from enrollment to 6-month follow-up, adjusting for patient, provider, and site characteristics. We will also construct multi-level mediation and moderation models to explore whether engagement-related factors such as patient activation, strength of treatment preferences, or the communication subscale of the CAHPS are associated with greater benefit from or satisfaction with care.

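### The comparison of risk-factor control and cardiac events by Gateway use is unadjusted, and its three groups leave some referred women with no group

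*Combined protocol and SAP*

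**What the plan says.** Section 5.6 (Quantitative Analysis) states for patients: "we will conduct bivariate analysis to examine variations in outcomes (CV risk factor control, cardiac event or procedure, etc". The contrast is between women who took part in Gateway "versus those who received a referral to a different program/service, and those who received no referral". No covariate or clustering term is named for this comparison. Nothing says where to put a woman who meets two of the descriptions, or none.

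The same section adjusts its other analyses. The stepped-wedge model estimates the effect of the "intervention on referral rates, while controlling for organizational level, provider level and patient level covariates". The mixed models for patient activation, quality of life and experience of care adjust for patient, provider and site characteristics.

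Section 5.1 (Site Selection, CV Toolkit, and REP Implementation Phases) describes how a woman reaches one group or another. "The patient and provider will collaboratively determine the next steps", and "the provider will document the action plan in the template". It adds: "All participants will be offered the *Gateway to Healthy Living* program by providers or other staff member". A woman counts as engaged in the "program when she attends the first group meeting". Section 5.1 (Adequacy of Protection from Risk) expects non-attendance; it explains the mailing of baseline surveys with "Since some patients may not attend the group immediately or at all".

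**The concern.** There are two separate problems.

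**Confounding.** Referral depends on what the woman and her provider decide, and participation depends on whether she then turns up. Women who attend may differ at baseline from those who do not, in the very risk factors being compared. A bivariate contrast carries that difference into the result. Attenders could look better or worse controlled at follow-up with no programme effect at all.

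**Group definition.** One group rests on participation and the other two on referral, so the three do not divide up the women. Followed literally, the plan leaves out women referred only to Gateway who did not attend, who may well be the less motivated ones. It also moves some Gateway non-attenders into the comparator. Two analysts with the same data could build different groups.

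At stake is how the clinical results are read. Section 5.6 promises inferential as well as descriptive statistics, and the toolkit is meant for wider dissemination, so a crude difference in risk-factor control or cardiac events is easily taken for a Gateway effect.

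**Working it through.** The plan states no sample size, power or event rate for this comparison, so there is no figure to reproduce. The only power result in section 5.6 is for referrals.

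**Step 1: set every possible state against the three definitions.**

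| State of the woman | Took part in Gateway | Referred elsewhere | No referral | Groups met |
|---|---|---|---|---|
| Referred to Gateway only, attended | yes | no | no | 1 |
| Referred to Gateway and elsewhere, attended | yes | yes | no | 2 |
| Referred to Gateway only, did not attend | no | no | no | 0 |
| Referred to Gateway and elsewhere, did not attend | no | yes | no | 1 (comparator) |
| Referred elsewhere only | no | yes | no | 1 |
| Not referred | no | no | yes | 1 |

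The third row has no group and the second has two. Section 5.1 anticipates the non-attendance behind the third row. It also has the facilitator record attenders' use of other services, so the second row is plausible too.

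**Step 2: an illustrative size for the grouping problem.** All inputs are assumptions, because the documents give none: g, the share of women with a Gateway referral, 0.3 to 0.5; o, the share of those referred to Gateway alone, 0.5 to 0.8; a, attendance among those referred, 0.3 to 0.6, taken as the same with or without another referral. Each formula is linear in each input, so its extremes lie at the ends of the ranges.

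- No group: g × o × (1 − a). From 0.3 × 0.5 × 0.4 = 6.0% to 0.5 × 0.8 × 0.7 = 28.0%.
- Two groups: g × (1 − o) × a. From 0.3 × 0.2 × 0.3 = 1.8% to 0.5 × 0.5 × 0.6 = 15.0%.
- No group or two groups: g × [o(1 − a) + (1 − o)a]. At o = 0.8 and a = 0.6 the bracket is 0.32 + 0.12 = 0.44; at o = 0.8 and a = 0.3 it is 0.56 + 0.06 = 0.62; at o = 0.5 it is 0.50 for any a. The range is 0.3 × 0.44 = 13.2% to 0.5 × 0.62 = 31.0%.
- Gateway non-attenders who fall in the comparator: g × (1 − o) × (1 − a). From 0.3 × 0.2 × 0.4 = 2.4% to 0.5 × 0.5 × 0.7 = 17.5%. These women fit exactly one group as written, so they are kept out of the total above.

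**Step 3: an illustrative size for the carry-over.** With no programme effect, the crude gap at follow-up is the baseline gap in control multiplied by [P(controlled at follow-up, if controlled at baseline) − P(controlled at follow-up, if uncontrolled at baseline)]. Assume a baseline gap of 5 to 20 points and a bracket of 0.3 to 0.6. The crude gap is then 5 × 0.3 = 1.5 to 20 × 0.6 = 12 points, in either direction.

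Worked example: baseline control 60% against 50%, with probabilities 0.80 and 0.35 in both groups. Follow-up control is 0.6 × 0.80 + 0.4 × 0.35 = 62.0% against 0.5 × 0.80 + 0.5 × 0.35 = 57.5%, a crude gap of 4.5 points. Within each baseline stratum the gap is 0.

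**Step 4: look for an adjusted model that covers these outcomes.** Section 5.6 has two sets of adjusted models. One is for referral rates; the other is for activation, quality of life and care experience. Neither covers risk-factor control or cardiac events by Gateway group.

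**The case against.** The best reply is that this is a modest descriptive analysis. The text proposes only to look at variation and makes no causal claim for the contrast. The toolkit itself is judged by the covariate-adjusted stepped-wedge model, and referrals are the powered outcome. That stands and limits the seriousness of the point. It leaves the grouping gap untouched, and it does not excuse an unlabelled crude comparison of clinical outcomes.

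A second reply is that setting Gateway participants against women referred to something different implies that Gateway comes first, which would make the groups exclusive. That is a natural reading, but the rule is not written, and with it the woman referred only to Gateway who does not attend would still have no group.

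A reader might also infer more than the documents support:

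- *That the no-referral group will be nearly empty because everyone is offered Gateway.* Section 5.1 treats offer and referral as different things. It lists waiting as one of the possible next steps and speaks separately of the women who are referred.
- *That the analysis population is wholly open.* Section 5.6 does not name it, but section 5.1 reserves the all-patient record data for roll-out and referral rates in aggregate, and section 5.5 takes utilisation from enrollees' records. Both point to enrolled women.
- *That the share misplaced is 15.6% to 42.5%*, from g × (1 − o × a). That total adds the non-attenders who were also referred elsewhere, and they fit one group as written.
- *That this belongs to the stated secondary aims.* Section 5.6 uses that term for activation, quality of life and care experience. This comparison is simply not the powered one.

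**Conclusion.** The point holds on the text. The comparison is unadjusted although membership is self-selected, and the three definitions leave at least one anticipated kind of patient without a group. It should be corrected before analysis, but it does not threaten the stepped-wedge evaluation of referrals.

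The size and direction of bias cannot be computed, because the documents give no referral, attendance or control rates. The 13.2% to 31% in no group or two, and the 1.5 to 12 points of carry-over, rest wholly on the assumed inputs shown; they indicate that the effect could be material, not that it will be. That some groups are undefined, and that no adjustment is planned for these outcomes, needs no assumption.

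**What to change.** 1. Use four exclusive, exhaustive groups, with Gateway taking priority: attended Gateway; referred to Gateway but did not attend; other referral only; no referral. Take referrals from CPRS and CDW, including the template, as section 5.1 (Study Design) already plans. Do not count the universal offer as a referral.
2. Make the main comparison of risk-factor control at follow-up a model adjusted for the baseline value of that risk factor in the medical record, age, and provider/site. Also report the contrast with the two Gateway groups combined. Keep the crude table as descriptive.
3. Analyse enrolled women whose survey is linked to their record, and start follow-up at the index visit in every group. Report cardiac events or procedures as counts by group if they are few.
4. Label the results associational.

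The cost is SAP wording and slightly more analysis. The record holds the referrals and baseline values, and section 5.5 already has Gateway use tracked. Some groups may be small and their contrasts imprecise. Combining the two Gateway groups dilutes any effect of attendance. A common start does not change the fact that attendance comes after it, so the split between attenders and non-attenders stays the weaker contrast. Confounding by motivation remains, which is why the label is needed even with adjustment.

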The CV Toolkit includes four elements: (1) Patient education/activation tools, such as informational posters and fliers about women's CV risk, including information about MyHealtheVet website resources. To activate patients to discuss CV risk with their providers, we developed a CV worksheet (Appendix 6) for patients to fill out at check-in to collect information about family history of CVD, pregnancy/gestational history, and smoking status, and to help patients formulate/document any questions regarding their CV risks that they would like to discuss during their visits. The goal is to help make CV risk discussion a priority for women before they enter the exam room. (2) A CV risk assessment computerized template systematically captures CVD risk factor history and data from the medical record, and provides open fields for the provider to enter any relevant information from the patient worksheet and the clinic visit (e.g., goals and decisions). The template also includes embedded links to locate CV guideline documents. Based on feedback from clinical teams at two GLA sites, the template includes data from the current visit as well as the last three entries in the medical record (automatically generated by the template) such as weight, blood pressure, and cholesterol lab results. This enables the provider to look at trends in risk factors without having to search the chart. The information is stored as a standard outpatient note in the patient's medical record (in CPRS) and is readily accessible (and searchable) at future visits so that CV risk status will be an ongoing discussion. Referral options are also included on the template, including referral to the *Gateway to Healthy Living* program, so the template will be a shared template available for other providers to access (e.g. health coach, dietitian, specialist, etc.) to review when the patient comes for the referral. (3) Provider information and education programs as well as referral tools to internal services (e.g., women's MOVE! program, smoking cessation clinics, dieticians, health coaches, pharmacists and CV or mental health specialists as needed). (4) The *Gateway to Healthy Living* program tailored to Women Veterans is a facilitated group meeting that occurs in a structured format with personalized goal setting and identification of key services available at the local site to assist with lifestyle changes necessary for patient-targeted CV risk reduction. In addition to the structured group, it includes at least two follow up phone calls from the facilitator (typically a health coach or health promotion disease prevention specialist) for support, reinforcement of lifestyle changes, brainstorming of barriers, and steps toward goal realization.

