### ***Veteran involvement and Characteristics***

This 4-site research project aims to implement and evaluate the CV toolkit designed to increase identification of CV risk among women Veterans, enhance patient/provider communication about CV risk, and increase women Veterans engagement and retention in relevant health services including referrals to key health programs. We will recruit adult women Veterans who visit their women's health provider at one of the four study sites if a CPRS CV risk template was activated from their primary care visit or they attended the Gateway to Healthy Living program. As long as the woman Veteran patient is also able to give informed consent to complete our protocol, she is eligible to participate. We expect to approach up to 200 women Veterans per site over the study period in order to achieve a minimum of 65 women participants in the survey/interviews for CV toolkit at each site. Our goal is to have 260 women total (minimum 65 per site across 4 sites) engaged in the project over the course of the study. Participation includes a brief survey at baseline and six-month post-baseline, and for a subset of women, a brief qualitative interview (approximately every third consented woman with a completed survey will be approached for an interview for a minimum of 20 patient interviews at a site). Women will be consented at the time of the survey and interviews. The women will also be consented to link their responses to their medical records at the time of the survey.

We will also use medical record data (CPRS template data and CDW data) to evaluate the roll-out of the intervention and the referral rates at all sites. This data will be evaluated for all women patients seen by the providers in the study over the study period. The data will only be evaluated in the aggregate and will not be linked to the patient survey or interview data (unless medical record access consent is received at the time of the survey).

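### Section 5.6 names cardiovascular risk-factor results only as control status, although measured values are held; baseline-adjusted measured values would mainly help the Gateway comparison

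*Combined protocol and SAP*

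**What the plan says.** Section 5.6 (Quantitative Analysis) plans two comparisons that touch cardiovascular risk itself.

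- **Patients.** A bivariate analysis of "variations in outcomes (CV risk factor control, cardiac event or procedure, etc" across three groups: Gateway participants, women referred elsewhere, and women with no referral.
- **Providers.** A comparison of patient panels by the provider's engagement with the toolkit, with this given as the example: "those with CV risk factors under control at follow-up".

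The section opens more generally, with "descriptive and inferential statistics to understand variations in the measures described above". It does not say which risk factors count, what thresholds define control, or at what time follow-up is read. It describes no analysis of a measured value.

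The measured values exist. Under Site Selection, CV Toolkit, and REP Implementation Phases, the template shows the current visit and the last three record entries, "automatically generated by the template) such as weight, blood pressure, and cholesterol lab results".

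Entry requires no raised risk factor. After template activation or Gateway attendance, the condition is: "As long as the woman Veteran patient is also able to give informed consent to complete our protocol, she is eligible to participate".

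**The concern.** Under control is ordinarily read as a yes/no status, that is, a cut through a continuous measurement. A woman already under control at baseline cannot improve on that scale. A woman well above a threshold can improve a good deal and still be counted as not controlled. Because entry does not depend on a raised risk factor, the first group may be large.

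These are the only named quantitative comparisons of risk-factor results. A real difference in blood pressure, cholesterol or weight between Gateway participants and others could be reported as no difference because of the scale chosen. Leaving control undefined also leaves the thresholds open to choice once data are seen.

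**Working it through.** **The plan's own figure.** The only power result is 8.78 (rounded to 9) referring PCPs per site for 0.80 power on the binary referral outcome. It cannot be reproduced, because the referral rates or effect size behind it are not given. It does not bear on this point. No power is stated for the risk-factor comparisons.

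**Inputs from the documents.** 260 women (65 per site); alpha 0.05; qualifying panels of at least 100 women; record data on all women seen by study providers.

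**Assumptions (not in the documents).** Two-sided test; normal measure; every Gateway woman shifted by d SD; proportion c of the comparison group under control, 50 to 80%; Gateway v no-referral sizes 65/130, 87/87 or 52/156; no dropout.

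**1. Efficiency of the cut.** Efficiency = φ(k)² / [c(1−c)], with k = Φ⁻¹(c). At c = 0.7, k = 0.524 and φ(k) = 0.348, so efficiency = 0.348² / 0.21 = 0.576. A comparison with 80% power on the measured scale then has power Φ((1.960 + 0.842)·√efficiency − 1.960).

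| c | Efficiency | 80% power becomes |
|---|---|---|
| 0.5 | 0.637 | 61% |
| 0.7 | 0.576 | 57% |
| 0.8 | 0.490 | 50% |

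**2. Gateway, 65 v 130, d = 0.4.**

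- Measured: 0.4·√(65·130/195) = 2.633; Φ(2.633 − 1.960) = 75%.
- Yes/no at c = 0.5: p₁ = Φ(0.4) = 0.655, p₂ = 0.5, difference 0.155; SE = √(0.655·0.345/65 + 0.25/130) = 0.0735; ratio 2.116; Φ(2.116 − 1.960) = 56%.
- Yes/no at c = 0.7 and 0.8: 50% and 43%.

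Over d = 0.3 to 0.5, the three splits and c = 0.5 to 0.8, the loss is 14 to 36 points. At d = 0.2 the same splits give 7 to 12 points, from a starting power of about 25%. At d = 0.15 the loss is 4 to 7. The upper end is not a ceiling: with a larger Gateway group (195 v 65, d = 0.4) a separate run gave 21 to 41 points.

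**3. Improvement confined to women not under control at baseline.** Simulation, 65 v 130, a 0.75 SD improvement in those women only, baseline/follow-up correlation 0.7. Ranges are over separate runs.

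| Under control | Measured, unadjusted | Yes/no cut, unadjusted | Measured, baseline-adjusted |
|---|---|---|---|
| 50% | 78% | 66% | 91% |
| 70% | 35–37% | 40–42% | 53% |
| 80% | 18% | 25–28% | 26% |

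Under a uniform shift, the baseline-adjusted analysis reached 96%, against 45 to 59% for the cut. With a weaker assumed correlation of 0.5 (87 v 87, d = 0.35), adjustment raises measured-scale power from 64% to 76%.

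**4. Provider panels.** Patients cluster within providers, so efficiency is multiplied by the ratio of design effects, taking the binary ICC as ICC × efficiency. For 100 women, ICC 0.02 and c = 0.5: the design effects are 1 + 99·0.02 = 2.98 and 1 + 99·0.02·0.637 = 2.26. Net efficiency is 0.637·2.98/2.26 = 0.84, and 80% power falls by 7 points.

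| Women per provider | ICC (assumed) | Loss from 80%, c = 0.5 to 0.8 |
|---|---|---|
| 100 | 0.01 | 10 to 18 |
| 100 | 0.02 to 0.05 | 4 to 13 |
| 250 | 0.01 | 6 to 11 |
| 250 | 0.02 to 0.05 | 2 to 7 |

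A loss of 15 to 29 points appears only if panels shrink to the enrolled women, about 260/36 = 7 per provider, with ICC 0.01 to 0.05.

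**The case against.** A reader might infer that the plan has decided to analyse risk factors solely as yes/no. The text does not go that far. The patient list is left open by its closing etc., the provider item is only an example, and control is never defined. What can be said is that control is the only form named and that no analysis of measured values is described.

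A reader might also carry the Gateway loss over to the provider panels. The panel calculation does not support that: between-provider variation dominates at 100 or more women, and the cut costs much less.

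Control fits the project's rationale, since the Abstract and Introduction frame the problem partly as worse control of risk factors in women. The stated aims are identification, communication, engagement and referral, so these comparisons are secondary. Both arguments stand. They lower the importance of the point but give no reason to leave the measured values unused.

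The strongest technical objection is that a uniform shift is itself doubtful when many women enter already controlled. The simulation bears this out: unadjusted measured values can do worse than the cut. With baseline adjustment, measured values beat the cut or come within about 2 points of it in every scenario run.

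Two further objections also stand. Blood pressure, cholesterol and weight do not cover smoking, which is not naturally continuous. And section 5.5 describes obtaining utilisation data but sets no follow-up window for blood pressure or lipids, so follow-up values cannot be assumed to be in hand.

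**Conclusion.** The point holds in a limited form. Control status is the only form in which section 5.6 names risk-factor results, while measured values with earlier entries are held. For the Gateway comparison, a yes/no cut costs roughly 14 to 36 points of power, conditional on about 260 women, a uniform shift of 0.3 to 0.5 SD and 50 to 80% under control. The documents supply neither the shift nor the control rate nor the group sizes. The loss shrinks with smaller shifts, and can vanish against an unadjusted continuous analysis if only women not under control improve. For panels of 100 or more women it is mostly 2 to 13 points, and up to 18 at ICC 0.01.

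A reader might conclude that the study is underpowered for its main question. That does not follow: the powered outcome is referral, which this leaves untouched. Nor does a continuous outcome make the Gateway comparison causal. The groups are self-selected, confounding remains on either scale, and it is a larger concern than the lost power.

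**What to change.** In section 5.6:

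- Analyse follow-up blood pressure, cholesterol and weight as measured values, each in a linear or linear mixed model adjusted for its baseline value. For provider panels, model the patients' values with clustering by provider.
- Keep percent under control as a companion result, with its risk factors, thresholds and time window fixed in advance. It also covers factors that are not continuous, such as smoking.
- Keep cardiac event or procedure as a binary outcome.
- Set the follow-up window for the extracted values, and describe the Gateway results as associations.

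The cost is wording, a defined extraction window and modest extra analysis, with no new patient measurements. The downside is several continuous outcomes in place of one label, so the plan should say how they will be read together.
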